2.2 Secondary Objectives

1) Further characterize the oncologic response to neo-adjuvant atezolizumab and adjuvant atezolizumab in combination with radiation therapy in patients with regionally metastatic HNSCCC:

- a) Determine the rate of major pathologic response (mPR) at the time of surgery.
- b) Evaluate the 2-year event free survival (EFS) after completion of adjuvant therapy.

2) Investigate the utility of conventional imaging and novel biomarkers in predicting and assessing response to neoadjuvant atezolizumab therapy.

- a) Investigate associations between pre-treatment tumor FDG avidity and response to neoadjuvant immunotherapy

- b) Evaluate the ability of fine-cut contrast enhanced CT or MRI of the head and neck to assess response to neoadjuvant immunotherapy prior to surgery.
- c) Evaluate the capabilities of serial liquid biopsy analysis of tumor-associated exosomes to predict neoadjuvant immunotherapy response.

3) Evaluate the safety and tolerability of anti-PD-L1 with atezolizumab neo-adjuvant therapy in resectable regional metastatic HNCSCC.

- a) Quantify Toxicity (adverse events) determined by CTCAE v5

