Because of the possibility of an initial increase in tumor burden caused by immune cell infiltration in the setting of a T-cell response (termed pseudoprogression) with atezolizumab treatment, clinical or radiographic progression per iRECIST may not be indicative of true disease progression. In the absence of unacceptable toxicity, patients with clinical or radiographic evidence of progression while receiving neo-adjuvant atezolizumab will be permitted to receive their second dose and postoperative adjuvant doses of atezolizumab if they meet all of the following criteria:

- Evidence of clinical benefit, as determined by the investigator following a review of all available data
- Absence of symptoms and signs (including laboratory values, such as new or worsening hypercalcemia) indicating unequivocal progression of disease
- Absence of decline in Performance Status that can be attributed to disease progression
- Absence of tumor progression at critical anatomical sites (e.g., leptomeningeal disease) that cannot be managed by protocol-allowed medical interventions

Patient who have NOT met all of the above criteria will NOT receive their second dose of neo-adjuvant atezolizumab and will proceed directly to surgery. These patients will also not receive adjuvant atezolizumab and will receive only SoC adjuvant radiation.

Pre-Dose Blood Draws

Participants will undergo blood draws at the infusion center prior to administration of neo-adjuvant atezolizumab for routine blood analysis as noted in section 5.1.5. One 4 mL lavender-top tube will be drawn simultaneously with these scheduled blood draws for research analysis of tumor-associated exosomes. This research vial will be transported by [name], [name], [name], or other approved Otolaryngology department members to the Cancer Center Biorepository for cataloging (contact: [name]), and storage as needed. Collected whole blood samples will be withdrawn and processed by [name] and collaborators when needed for subsequent analysis.

Post-neo-adjuvant Imaging

Repeat fine-cut contrast-enhanced CT or MRI imaging of the head and neck will be performed one week prior to surgery to assess response to neo-adjuvant therapy. The imaging modality utilized will be the same as that modality used for screening.

Surgery and Pathologic Evaluation

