All participants will undergo a curative-intent surgical resection as defined by SoC. Surgery will occur within 10 weeks of study enrollment and at least two weeks after second dose of neoadjuvant Atezolizumab. The goal of curative intent surgery for regionally metastatic CSCC involves resection to negative margins of the index lesion with the associated at-risk regional lymph nodes as determined by the study physician. An evaluation of tumor status and staging per AJCC guidelines (8th edition) will be performed on all surgical specimen. The pathologist will assess the specimen for pCR and mPR (see 10.1). Pathology assessment will be as per standard of care documentation, including: dimensions of index lesion, total nodal number of lymph nodes removed, total positive node number (and positive nodal levels), any extracapsular extension, any perineural invasion. PD-L1 staining will be performed on a representative section from the largest positive node. Tissue will be formalin fixed and paraffin embedded and banked per standard pathology protocol.

Patients demonstrating pCR at time of surgery:*Adjuvant Treatment*

Patients demonstrating pCR at the time of surgery will not receive any additional adjuvant therapy and will enter surveillance.

Imaging

PET/CT will be performed approximately 12 weeks after surgery.

Follow-up / Surveillance

Patients will be followed in otolaryngology/head and neck surgery and medical oncology clinic every 3 months for 3 years after surgery. Patients will be assessed for treatment-related side effects, cancer recurrence and blood draws performed at the cancer center for biomarkers.

In the setting of suspected clinical or radiographic recurrence per iRECIST criteria, tumor tissue will be collected by biopsy, unless not clinically feasible as assessed and documented by the investigator.

Patients with residual disease at time of surgery:

Patients with residual disease at the time of surgery will receive atezolizumab Q3W x 15 cycles in combination with SoC adjuvant radiation. SoC adjuvant radiation will be initiated greater than 4 weeks and less than 7 weeks after surgery and consists of 6 weeks of radiation therapy with dosimetry determined by pathologic findings at the time of surgery. Recommendations for adjuvant treatment will be determined at a multidisciplinary tumor board where surgical pathology findings will be reviewed. Adjuvant atezolizumab will begin concurrent to adjuvant radiation and continue for 15 cycles.

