Pre-Dose Blood Draws

As in the neo-adjuvant setting, participants will undergo blood draws at the infusion center prior to administration of adjuvant atezolizumab for routine blood analysis as noted in section 5.1.5. One 4 mL lavender-top tube will be drawn simultaneously with these scheduled blood draws for research analysis of tumor-associated exosomes. This research vial will be transported by [name], [name], [name], or other approved Otolaryngology department members to the Cancer Center Biorepository for cataloging (contact: [name]), and storage as needed. Collected whole blood samples will be withdrawn and processed by [name] and collaborators when needed for subsequent analysis.

Imaging

All participants will have imaging performed with PET/CT approximately 12 weeks after completion of adjuvant RT.

Follow-up / Surveillance

Patients will be followed in otolaryngology/head and neck surgery and medical oncology clinic every 3 months for 2 years after completion of adjuvant atezolizumab. Patients will be assessed for treatment-related side effects, cancer recurrence and blood draws for biomarker. In the setting of suspected clinical or radiographic recurrence per iRECIST, tumor tissue will be collected by biopsy, unless not clinically feasible as assessed and documented by the investigator.

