5.1.4 Tumor and Response Evaluations

Patients will undergo tumor assessments at baseline, every 2 weeks following treatment initiation up to the date of surgery. After surgery they will be assessed at 1 week and 1 month postoperatively, and no longer an interval than every 3 months thereafter, regardless of dose delays, until radiographic disease recurrence/progression per iRECIST or two years have passed since completion of adjuvant treatment. Thus, tumor assessments are to continue according to schedule in patients who discontinue treatment for reasons other than disease progression or loss of clinical benefit, even if they start new anti-cancer therapy. At the investigator's discretion, tumor assessments may be repeated at any time if progressive disease is suspected.

All measurable and evaluable lesions should be assessed and documented at screening. Tumor assessments performed as standard of care prior to obtaining informed consent and within 28 days prior to initiation of study treatment do not have to be repeated at screening.

Screening assessments must include contrasted CT or MRI scans of the head and neck as well as a PET CT. A spiral CT scan of the chest may be obtained but is not a requirement. If a CT scan with contrast is contraindicated (e.g., in patients with impaired renal clearance), a non-contrast CT scan of the chest may be performed. At the investigator's discretion, other methods of assessment of measurable disease as per iRECIST may be used.

All measurable and evaluable lesions identified at baseline should be re-assessed at each subsequent tumor evaluation. The same radiographic procedures used to assess disease sites at screening should be used for subsequent tumor assessments.

Overall response at a single timepoint will be assessed by the investigator using iRECIST (see Section 15.9) after the two neoadjuvant doses. Assessments should be performed by the same evaluator, if possible, to ensure internal consistency across visits.

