10. STATISTICAL CONSIDERATIONS

10.1 Study Design and Overview of Primary and Secondary Endpoints

This is a Phase II single-arm trial investigating the efficacy of the anti-PD-L1 antibody atezolizumab (Genentech) in the neoadjuvant setting for patients with regionally metastatic cutaneous head and neck squamous cell carcinoma with a historic or unknown primary. This will be an open-label trial reporting response rates with pCR as the primary endpoint.

Due to the nature of single arm and small sample size, we will not adjust our analyses for multiplicity, but we will present all outcomes we studied in the single paper with pre-specified designation of each outcome (e.g., primary or secondary/exploratory). Also, formal hypothesis testing will be avoided or properly accompanied/indicated by warning (e.g., a historical control for comparator or other comparability issues).

We will summarize continuous data at baseline with standard descriptive statistics, e.g., mean and SD (or median and IQR) and binary data with frequency and proportion. For continuous and binary outcomes data, point estimates and 95% CIs will be computed for appropriate parameter estimable (e.g., mean or median with accounting for censoring, if needed) and the Clopper and Pearson exact binomial method (with no censoring), respectively.

Primary Endpoints

Pathologic Complete Response (pCR)

pCR is defined as having no residual invasive squamous cell carcinoma within the primary tumor and all resected lymph nodes as assessed by the pathologist at the time of primary resection. The rate of pCR is defined as the proportion of patients demonstrating pCR.

Major Pathologic Response (mPR)

mPR is defined as having $\leq 10\%$ residual invasive squamous cell carcinoma within the primary tumor and all resected lymph nodes as assessed by the pathologist at the time of primary resection. The rate of mPR is defined as the proportion of patients demonstrating mPR.

Event Free Survival (EFS)

EFS is defined as the time from randomization to the first day of the any of the following events:

- Radiographic evidence of recurrence or disease progression per iRECIST
- Clinical evidence of recurrence or disease progression as assessed by clinical exam and confirmed by biopsy.
- Death due to any cause

A non-parametric Kaplan-Meier (KM) method will be used to estimate the 2-year EFS curve. Participants who do not experience recurrence or disease progression at the time of their last

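### EFS is timed from a randomization that this single-arm trial does not have, and objective 1b does not supply an origin that every patient has

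*Combined protocol and SAP*

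**What the plan says.** Section 10.1 begins "This is a Phase II single-arm trial" and further on defines the endpoint: "EFS is defined as the time from randomization to the first day of the any of the following events". The events are radiographic recurrence or progression per iRECIST, clinical recurrence or progression confirmed by biopsy, and death from any cause. A Kaplan-Meier estimate at two years is planned. The section then handles 2-year disease-free, overall and disease-specific survival in the same way and gives no other start date for them. Sections 3.3.4 and 10.1 plan an informal comparison with historical controls from the institution; neither states the controls' time origin.

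Objective 1b, in the synopsis and in section 2.2 Secondary Objectives, reads: "Evaluate the 2-year event free survival (EFS) after completion of adjuvant therapy". The endpoint lists in the synopsis and in section 2.2 Endpoints say only that EFS is a 2-year measure. Section 10.1 prints the definition beneath a heading for primary endpoints, but the synopsis and section 2 class EFS as secondary, and it is treated as secondary here.

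Section 3.1 sets out three routes after surgery:
- With pCR: "Patients demonstrating pCR at the time of surgery will not receive any additional adjuvant therapy and will enter surveillance".
- With residual disease: 15 three-weekly cycles of atezolizumab, started together with radiation.
- After progression in the neoadjuvant period without meeting the criteria for continuing: "These patients will also not receive adjuvant atezolizumab and will receive only SoC adjuvant radiation".

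Follow-up is anchored differently by route. pCR patients are seen for three years from surgery. Residual-disease patients are seen "every 3 months for 2 years after completion of adjuvant atezolizumab". Under section 5.1.4, tumor assessments run until recurrence or progression, or until "two years have passed since completion of adjuvant treatment". The section 6 calendar labels enrollment as Day 0, but no text connects that day to EFS.

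**The concern.** A time-to-event endpoint needs a start date that exists for every patient analysed. The one given here exists for none, so the definition cannot be applied as written. An analyst must choose a substitute, and the protocol points in several directions: enrollment is Day 0 of the calendar, first dose is the start of treatment, surgery anchors follow-up for pCR patients, and the end of adjuvant treatment appears in objective 1b and anchors follow-up for the others. Each gives a different quantity under the same name.

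At stake are the meaning of the 2-year EFS figure, the three further 2-year survival figures derived the same way, and the description against historical controls. If the origin is settled only after outcomes are known, the choice is open to the criticism that it was made with the data in view.

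**Working it through.** The documents give no EFS target, event count or power, so there is no EFS figure to reproduce. The check has two parts: whether objective 1b can serve as the origin, and how far apart the candidate 2-year marks lie.

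**1. Can objective 1b supply the origin?**

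| Route (section 3.1) | Date on which adjuvant therapy is complete |
|---|---|
| pCR at surgery | None; no adjuvant therapy is given |
| Residual disease | End of atezolizumab, well after radiation ends |
| Radiation only | End of radiation |

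The phrase has no value on the first route and means different events on the other two. By the success rule (synopsis and section 10.2), a positive trial has at least 3 pCR patients, each without this date. At the design alternative the expected number is 18 × 0.30 = 5.4 of 18.

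**2. When does adjuvant treatment end?** Weeks are counted from enrollment, with the first dose taken at enrollment for the lower limits and no interruptions.

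Inputs:
- Surgery (section 3.1): "Surgery will occur within 10 weeks of study enrollment and at least two weeks after second dose of neoadjuvant Atezolizumab". With doses three weeks apart, the earliest is 3 + 2 = 5 weeks; the latest is 10.
- Adjuvant start (section 3.1; section 6, footnote 6): more than 4 and less than 7 weeks after surgery.
- Dose 15 falls 14 × 3 = 42 weeks after adjuvant dose 1.
- Radiation lasts 6 weeks.

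Results:
- Last atezolizumab dose: 5 + 4 + 42 = 51 to 10 + 7 + 42 = 59 weeks.
- End of radiation after two neoadjuvant doses: 5 + 4 + 6 = 15 to 10 + 7 + 6 = 23 weeks. It can be earlier if the second dose is withheld.

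The lower limit depends on which text is followed. The nominal calendar puts imaging five weeks after the first dose, and section 3.1 puts imaging one week before surgery. That places surgery at 6 weeks and the last dose at 6 + 4 + 42 = 52. The synopsis describes an adjuvant start at 6 to 7 weeks, which would add 2 weeks to the lower limits. The upper limits are not maxima, because section 7.4 allows atezolizumab to be withheld for 12 weeks or longer.

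**3. Candidate 2-year marks**
- From enrollment: 104 weeks.
- From the last atezolizumab dose: 51 + 104 = 155 to 59 + 104 = 163 weeks.

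The gap is 51 to 59 weeks, about one year. Progression, recurrence or death during that year counts as an event under section 10.1 but would precede time zero if objective 1b set the origin.

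**4. Does planned follow-up reach 104 weeks from enrollment?**
- pCR: 5 + 156 = 161 to 10 + 156 = 166 weeks.
- Completed adjuvant atezolizumab: at least 155 weeks.
- Radiation only, by section 5.1.4: at least 15 + 104 = 119 weeks after two neoadjuvant doses. With the second dose withheld it is still more than 104, since adjuvant treatment ends after enrollment.

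**The case against.** The strongest reply is that objective 1b was never meant as time zero. It may describe how long patients are watched. The follow-up plan supports that: measured from surgery, residual-disease patients are followed for 4 + 42 + 104 = 150 to 7 + 42 + 104 = 153 weeks (153 to 156 if counted from the end of cycle 15), close to the 156 weeks given to pCR patients. The sponsor may therefore have had a horizon of about three years in mind. This stands as a plausible reading, but a horizon is not an origin, so the definition remains unusable. It does show that rewriting objective 1b as 2-year EFS from enrollment would be more than an editorial correction: against a post-adjuvant reading, the mark moves about a year earlier.

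A second reply is that anyone would substitute enrollment. The text does not settle this. Section 3.1 has patients enrolled at the initial clinical evaluation, section 11.3 registers them only after pretreatment evaluations, and the calendar places Day 0 after screening. A reader might also infer that registration and first dose are interchangeable, because section 15.3 allows registration up to 72 hours before treatment. Section 7.5 does not support that: if the cycle 1 criteria are not met, the patient is re-evaluated weekly and the first dose can slip.

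A third reply is that EFS is secondary and descriptive, with about 18 patients. That is correct and limits the weight of the point.

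**Conclusion.** The definition is wrong as written. Its time origin exists for no patient, and objective 1b does not repair it on either reading. On an uninterrupted schedule the candidate 2-year marks differ by about one year (51 to 59 weeks, or 52 at the lower end on the nominal calendar). The other 2-year survival estimates inherit the gap. It should be fixed before outcomes are analysed, but it does not touch the pCR decision or the Simon design.

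Two stronger conclusions are tempting and are not supported:
- A reader might infer a shift of 9 to 10 points in 2-year EFS. A constant hazard through the 53.2% 5-year disease-free survival in section 3.3.3 gives 77.7% at 2 years and 68.7% to 67.4% at 2.98 to 3.13 years. That compares two horizons from one origin. Under the same hazard, 2-year EFS counted from adjuvant completion among patients still event-free is again 77.7%, a difference of zero. The real hazard shape is unknown, so neither size nor direction of bias is established.
- A reader might infer that at least 3/18 = 17% of all enrolled patients lack an adjuvant-completion date in a successful trial. Section 5.3 replaces patients who stop study treatment early, so the number enrolled may exceed 18. The count of 3 stands for a positive trial; the percentage is not a floor.

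**What to change.** - In section 10.1, replace randomization with one dated origin that every patient has: either registration/enrollment (Day 0 of the calendar, stated to be the registration date of section 11.3) or the first atezolizumab dose. State that the same origin applies to 2-year disease-free, overall and disease-specific survival.
- Reword objective 1b in the synopsis and section 2.2 to that origin. The sponsor should confirm that two years from it is the intended horizon, since this settles the estimand.
- Report any estimate counted from surgery or from the end of adjuvant therapy as a supportive landmark analysis with its own denominator.
- State the time origin used for the historical controls, and report any mismatch with the trial's origin as a limitation.

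The cost is a short amendment and one sponsor decision. No extra visits are needed, because planned follow-up already passes two years from enrollment on each route. The downsides are that early events now count, so reported EFS may be lower; that the 2-year mark comes earlier than on a post-adjuvant reading; and that aligning the historical controls may need some data work.

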Biopsies at the time of recurrence/progression should be performed within 40 days after progression or prior to the next anti-cancer therapy, whichever is sooner. Samples collected via resection, core-needle biopsy (at least three cores preferred), or excisional, incisional, punch, or forceps biopsy are preferred.

Exploratory biomarker research may include, but will not be limited to: analysis of genes or gene signatures associated with tumor immunobiology, PD-L1, lymphocyte subpopulations, T-cell receptor repertoire, or cytokines associated with T-cell activation. Research may involve extraction of DNA, circulating tumor DNA, or RNA, or exosomes, analysis of mutations, and genomic profiling through use of next-generation sequencing (NGS) of a comprehensive panel of genes. Research will aim to distinguish germline mutations from somatic mutations. NGS methods may include whole exome sequencing (WES) or whole genome sequencing (WGS).

Unless the patient gives specific consent for his or her leftover samples to be stored for optional exploratory research, biological samples will be destroyed when the final Clinical Study Report has been completed, with the following exceptions:

- Blood samples collected for WGS or WES will be stored until they are no longer needed or until they are exhausted. However, the storage period will be in accordance with the IRB/EC approved Informed Consent Form and applicable laws (e.g., health authority requirements).
- Blood, plasma, serum, tumor tissue samples collected for biomarker research will be destroyed no later than 5 years after the final Clinical Study Report has been completed.

When a patient withdraws from the study, samples collected prior to the date of withdrawal may still be analyzed, unless the patient specifically requests that the samples be destroyed or local laws require destruction of the samples. However, if samples have been tested prior to withdrawal, results from those tests will remain as part of the overall research data.

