5.3 Treatment and Patient Discontinuation

Patients must permanently discontinue study treatment (atezolizumab) if they experience any of the following:

- Intolerable toxicity related to study treatment, including development of an immune-mediated adverse event determined by the investigator to be unacceptable given the individual patient's potential response to therapy and severity of the event
- Any medical condition that may jeopardize the patient's safety if he or she continues study treatment
- Investigator discretion
- Use of another non-protocol anti-cancer therapy
- Pregnancy
- Loss of clinical benefit as determined by the investigator after an integrated assessment of radiographic and biochemical data, local biopsy results (if available), and clinical status (e.g., symptomatic deterioration such as pain secondary to disease). In the adjuvant setting, any documented recurrence of tumor will be considered a treatment failure qualifying the patient for discontinuation of the study

The primary reason for study treatment discontinuation should be documented in the patient's medical records. Patient who discontinue treatment will be proceed with SoC treatment. In the neo-adjuvant setting, patient will proceed to definitive surgery with or without adjuvant therapy. In the adjuvant setting, patients will complete their adjuvant course of adjuvant radiation or chemoradiation or continue with routine surveillance. Patients who discontinue study treatment prematurely will be replaced.

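### A clinical recurrence with neither biopsy nor iRECIST imaging is not an EFS event under 10.1, although 3.1 allows the biopsy to be omitted; if it is censored, 2-year EFS is biased upward

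*Combined protocol and SAP*

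**What the plan says.** Section 10.1 lists three alternative EFS events:

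- "Radiographic evidence of recurrence or disease progression per iRECIST", with no biopsy condition;
- "Clinical evidence of recurrence or disease progression as assessed by clinical exam and confirmed by biopsy";
- "Death due to any cause".

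The censoring rule in 10.1 applies to "Participants who do not experience recurrence or disease progression at the time of their last" follow-up. It does not say whether an unconfirmed clinical recurrence counts as a recurrence for this purpose.

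Section 3.1, for patients with pCR and for those with residual disease, says that when clinical or radiographic recurrence is suspected "tumor tissue will be collected by biopsy, unless not clinically feasible as assessed and documented by the investigator".

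Section 5.3 says that in the adjuvant setting "any documented recurrence of tumor will be considered a treatment failure qualifying the patient for discontinuation of the study". No biopsy is required there. The list containing that sentence opens with "Patients must permanently discontinue study treatment (atezolizumab) if they experience any of the following".

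On timing, 5.1.5 says "Biopsies at the time of recurrence/progression should be performed within 40 days after progression", or before the next anti-cancer therapy if that is sooner.

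**The concern.** The protocol foresees recurrences that will not be biopsied, but the EFS definition has no place for one that was found only on examination. During adjuvant treatment the same patient can be a treatment failure under 5.3 and have no EFS event under 10.1. If the analyst then censors that patient, the censoring happens because the disease has come back. Kaplan-Meier estimation assumes that censoring carries no such information, so the estimate would be too favourable. The 2-year EFS will be described beside historical controls (3.3.4 and 10.1), so an upward shift would flatter the trial in that comparison.

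The event date is a smaller gap. Section 10.1 runs EFS to the first day of the event, but for a biopsied clinical recurrence it does not say whether that is the day of the examination or of the biopsy, which may be up to 40 days later.

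**Working it through.** **Does imaging close the gap?** The plan states no EFS target, event count or power, so there is no figure to reproduce. The texts have to be compared.

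1. Section 5.1.4 asks for tumor assessments at least every 3 months after surgery, with the radiographic procedures used at screening.
2. The study calendar (section 6) marks no head and neck CT or MRI after surgery, and one PET, at the 3-month follow-up visit only.
3. Extra assessment on suspicion of progression is at the investigator's discretion (5.1.4).
4. Section 5.1.4 explicitly continues scheduled assessments for patients who stop treatment for reasons other than progression or loss of clinical benefit. The patient at issue is outside that assurance.

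Imaging will therefore often capture the recurrence, but the text does not ensure it.

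**Size, as an illustration.** Inputs: N = 18 (synopsis and 10.2). D = recurrences within 2 years and k = those not counted; both are assumptions. One anchor for D is the institutional 5-year disease-free survival of 53.2% in 3.3.3. With a constant hazard, 0.532^(2/5) = 0.777 at 2 years, and 18 × (1 − 0.777) = 4.0 recurrences. Everyone else is assumed event-free and followed to 2 years, with no ties.

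- All recurrences counted: (18 − D)/18.
- The k earliest recurrences censored when found: (18 − D)/(18 − k), the lower end.
- The k latest censored when found: (18 − D + k)/18, the upper end. The same value results if the k patients stay under follow-up past 2 years with no event recorded.

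| D | All counted | k = 1 | k = 2 |
|---|---|---|---|
| 4 | 14/18 = 0.778 | 14/17 to 15/18 = 0.824 to 0.833 | 14/16 to 16/18 = 0.875 to 0.889 |
| 5 | 13/18 = 0.722 | 13/17 to 14/18 = 0.765 to 0.778 | 13/16 to 15/18 = 0.813 to 0.833 |
| 6 | 12/18 = 0.667 | 12/17 to 13/18 = 0.706 to 0.722 | 12/16 to 14/18 = 0.750 to 0.778 |
| 8 | 10/18 = 0.556 | 10/17 to 11/18 = 0.588 to 0.611 | 10/16 to 12/18 = 0.625 to 0.667 |

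The shift for one uncounted recurrence runs from 10/17 − 10/18 = 3.3 points (D = 8, earliest) to 1/18 = 5.6 points (latest, any D). It is zero if the recurrence is also recorded on imaging per iRECIST. In this set-up it is also zero at 2 years if the patient dies within 2 years and the death is counted.

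**The case against.** Three stronger readings are tempting, and the documents do not support them.

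- *That the plan censors such a patient as event-free.* It does not say so. The rule censors patients without recurrence, and an evident recurrence does not plainly fit that wording. The handling is unstated; censoring is one likely result of applying the event list literally.
- *That 5.3 removes the patient from the study.* The sentence covers only the adjuvant setting, speaks of qualifying for discontinuation, and stands in a list about stopping atezolizumab. The same section foresees continued routine surveillance. It does not clearly reach patients with pCR, who receive no adjuvant therapy, or patients in surveillance afterwards.
- *That cause of death is not collected.* Section 8 requires it for deaths during the trial or within 30 days of stopping treatment, and 9.5.2.6 asks for all later deaths to be reported. What remains open is how far this extends to a patient regarded as having left the study at recurrence.

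The best case against the point itself is that it needs three things together: a recurrence found only on examination, a biopsy documented as infeasible, and no qualifying scan. That is likely to be uncommon. EFS is secondary and descriptive; with 13 of 18 patients event-free the exact 95% interval runs from 46.5% to 90.3%, so a shift of a few points changes no planned decision. Section 10.1 also plans a disease-free survival estimate from recurrence with no biopsy condition stated, where such a case may appear. Finally, the protocol itself warns of pseudoprogression (3.1, 3.3.5), which is a reason to want confirmation.

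All of this limits the weight of the point. It does not supply the missing rule, and a wide interval does not excuse an avoidable bias in a known direction.

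**Conclusion.** The point holds as a gap between sections. As 10.1 is written, a clinical recurrence with neither biopsy nor iRECIST imaging is not an EFS event and may be censored at last follow-up, although 3.1 foresees that the biopsy may be missing and 5.3 treats a documented recurrence in the adjuvant setting as a failure. If censored, each such case raises 2-year EFS by roughly 3 to 6 points with 18 patients. That range rests on assumed totals of 4 to 8 recurrences, full follow-up of everyone else, and an assumed number of uncounted cases. The direction does not depend on those numbers. The dating question concerns at most 40 days per biopsied case. The pCR endpoint, the two-stage rule and the sample size are untouched. It is worth correcting before outcomes are known, because the trial is open-label and the investigator documents whether a biopsy is feasible.

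**What to change.** In 10.1:

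- Extend the second EFS event to a clinical recurrence or progression that the investigator documents where biopsy is recorded as not feasible under 3.1.
- Date every clinical recurrence from the examination at which it was first found, whether or not a biopsy follows.
- Add a sensitivity analysis that counts only deaths and recurrences confirmed by biopsy or by imaging per iRECIST, and state the censoring date used there for unconfirmed cases.

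Separately, reconcile 3.1, 5.1.4, 5.3 and section 8 on whether outcome data, including cause of death, continue to be collected after recurrence. In 5.3 the heading of the list speaks of stopping study treatment, while the sentence on recurrence speaks of discontinuing the study; the sponsor needs to settle which is meant.

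The cost is a few sentences and one extra analysis, with no new procedure for patients under the 10.1 changes. The downside is that some unconfirmed examination findings may be counted, so reported EFS may be slightly lower; the sensitivity analysis shows by how much.
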